#### LIST OF ABBREVIATIONS

ANCOVA Analysis of covariance

 $AUC(0-\infty)$  Area under the concentration of active substance—time curve in the time interval

from zero (before taking the drug) to infinity

AUC(0-t) Area under the concentration of active substance—time curve in the time interval

from zero (before taking the drug) to the last detected concentration of the drug

Cmax Maximum concentration of the active substance CTCAE Common Terminology Criteria for Adverse Events

GCP Good Clinical Practice

HAQ Health assessment questionnaire

HbsAg Hepatitis B surface antigen

HCV Hepatitis C virus

LLoQ Lower limit of quantification LOCF Last observation carried forward

T½ Half-life related to the terminal phase of the PK curve tmax

Time to maximum concentration of the active substance

SUSAR Suspected unexpected serious adverse reaction

ALT Alanine aminotransferase AST Aspartate aminotransferase

APTT Activated partial thromboplastin time

VAS Visual Analogue Scale ULN Upper Limit of Normal

HIV Human Immunodeficiency Virus

WHO World Health Organization

GGT Gamma-glutamyl transpeptidase

IL Interleukin

BMI Body mass index CRF Case Report Form

LDH Lactate dehydrogenaseHDL High-density lipoproteinsLDL Low-density lipoproteins

INR International normalized ratio
INN International nonproprietary name

ADR Adverse Drug Reaction

NSAID Nonsteroidal anti-inflammatory drug

AE Adverse event

SAE Serious adverse event

ESR Erythrocyte sedimentation rate

(hs) CRP (high-sensitivity) C-reactive protein

PK Pharmacokinetics
TNF Tumor necrosis factor

HCG Human chorionic gonadotropin

CONFIDENTIAL P. 8 of 84

ALP Alkaline phosphatase ECG Electrocardiogram

CONFIDENTIAL P. 9 of 84

# 2 PROTOCOL SYNOPSIS

Sponsor Name: R-Pharm International LI	LC C
Investigational medicinal product provided by the Sponsor: RPH-104/L04018	
Name of the active ingre RPH-104/L04018	edient:
Study title:	An Open-label, Single-dose, Active-controlled Randomized Phase IIa Clinical Study to Evaluate the Safety, Tolerability, Pharmacokinetics and Pharmacodynamics of RPH-104 (L04018) Administered at Different Doses to Patients With Acute Gout Attack
Study sites:	Approximately 19 sites in the Russian Federation
Clinical study phase:	IIa
Study goal and	Study goal:
objectives:	To evaluate the efficacy, pharmacokinetics, pharmacodynamics, safety and tolerability of RPH-104 following a single injection in adult patients with an acute gout attack.
	Objectives:
	• To investigate the efficacy of RPH-104 in the treatment of an acute gout attack following a single subcutaneous injection at doses of 4, 20, 40, 80 and 160 mg;
	To investigate the pharmacokinetics of RPH-104 following its single subcutaneous injection;
	
 
To investigate the effect of RPH-104 following its single subcutaneous injection on concentrations of high-sensitivity C-reactive protein (hs-CRP), serum amyloid protein, blood cytokines (IL-1α, IL-1β, IL-1RA, IL-6, IL-8, TNF-α);
 

	
 
To investigate the safety parameters of RPH-104 in adult patients with an acute gout attack.
 

Study methods:	A multicenter, randomized, parallel group, single-dose, phase IIa, open-label study of the sponsor's investigational product to evaluate its efficacy, pharmacokinetics, pharmacodynamics, and safety.
	It is planned to enroll patients in two periods: in the first period, it is planned to randomize 7 patients for treatment with the reference product Voltaren® (diclofenac) and 15 patients for treatment with RPH-104 4 mg; in the second period, it is planned to randomize 7 patients into the reference product Voltaren® (diclofenac) group and 56 patients into the RPH-104 groups at doses of 20 mg, 40 mg, 80 mg and 160 mg, 14 patients in each group.
Number of patients:	
Number of patients participating in the study enrollment procedures:	up to 135
Patients treated with investigational product therapy:	85
In each treatment	treatment with RPH-104: 15 patients – 4 mg, 14 patients – doses of 20 mg, 40

CONFIDENTIAL P. 14 of 84

Sponsor Name: R-Pharm International LL	С		
Investigational medicina	nvestigational medicinal product provided by the		
Sponsor: RPH-104/L04018			
Name of the active ingre RPH-104/L04018	edient:		
group:	mg, 80 mg, 160 mg therapy with Voltaren® (diclofenac): 14 patients		
Primary diagnosis:	Acute gout attack		
Main eligibility criteria:	Male and female patients aged 18 to 80 years with an acute gout attack that occurred within not more than 120 hours (5 days) before randomization, with at least one painful joint at screening with pain intensity of 50 mm and more on a 100 mm visual analogue scale (VAS) for pain intensity assessment.		
Investigational product provided by the Sponsor:	RPH-104, solution for subcutaneous injection, 40 mg/ml		
Doses:	4, 20, 40, 80, 160 mg		
Route of administration:	For doses 4, 20, 40, 80 mg – subcutaneously, once. A 160 mg dose is divided into two injections, 80 mg each at different injection sites.		
Reference product:	Voltaren® (diclofenac), enteric-coated tablets		
Doses:	50 mg and 25 mg		
Route of administration:			
Rescue therapy:			
	the first use of the investigational product to intensify therapy. The rescue medication is triamcinolone 40 mg intramuscularly. If an attack recurs after the use of the rescue medication, treatment is carried out in accordance with the standard practice of the hospital.		
Concomitant therapy:	In order to prevent damage to the gastric and duodenal mucosa caused by Voltaren® (diclofenac), all patients receiving Voltaren® (diclofenac) will simultaneously take Ortanol® (omeprazole) as follows: 20 mg, orally daily before breakfast throughout the course of Voltaren® (diclofenac) treatment. On the first day of therapy in the study, it is possible to take it regardless of meals and at a later time.		
	Method of administration of Ortanol® (omeprazole): orally, with a sufficient amount of liquid.		
Duration of treatment:	Treatment with RPH-104: single dose (a 160 mg dose is divided into two injections, 80 mg each at different injection sites.		
	therapy with Voltaren® (diclofenac): 12 days		
Evaluation criteria:			
Primary efficacy variable	Change in pain intensity in the assessed joint at 72 hours after start of the investigational product therapy compared to baseline, as measured on the visual analogue scale (VAS).		
Other efficacy variables:	• Change in pain intensity in the assessed joint at 15, 30, 45 minutes, 1, 1.5, 2, 4, 8, 24, 48, 72 hours, on days 5, 6, 10, 15, 18, 22, 29 and 45 after start of the investigational product therapy compared to baseline (as measured on VAS).		
	
 
Proportion of patients who rated the response to the investigational product therapy as "Excellent" or "Good" at 15, 30, 45 minutes, 1, 1.5
 
		

CONFIDENTIAL P. 15 of 84

Sponsor Name: R-Pharm International LL	.C
Investigational medicinal product provided by the Sponsor: RPH-104/L04018	
Name of the active ingre RPH-104/L04018	edient:
	hours, 2, 4, 8, 24, 48, 72 hours, on days 5, 6, 10 15, 18, 22, 29, and 45 after initiation of the investigational product therapy;
	• Change in the degree of swelling, tenderness, erythema in the assessed joint at 24, 48, 72 hours, on days 5, 6, 10, 15, 18, 22, 29 and 45 after start of the investigational product therapy compared to baseline;
	• Change in movement restriction in the assessed joint at 24, 48, 72 hours, on days 5, 6, 10, 15, 18, 22, 29 and 45 after start of the investigational product therapy compared to baseline;
	• Time to 50% reduction in pain intensity in the assessed joint relative to the baseline level according to the VAS;
	Time to use of the rescue medication;
	• The proportion of patients who received the rescue medication within 72 hours of starting the investigational product therapy and over the entire treatment period;
	
 
Changes in the health assessment questionnaire (HAQ) scores 15, 29, and 45 days after start of the investigational product therapy compared to baseline.
 

Pharmacokinetic variables:	Blood samples for pharmacokinetic assessment will be collected from patients who have received RPH-104 at the following times: before RPH-104 administration, at 2, 8, 24, 48, 72, 96, 120, 216, 336, 408, 504, 672, 1056 hours after the investigational product administration.
	Pharmacokinetic parameters of subcutaneous RPH-104: AUC0-t, AUC0-∞, Cmax, tmax, t1/2, Kel.
Immunogenicity vairables:	Blood samples for immunogenicity assessment will be collected from patients treated with RPH-104 at the following time points: before administration of RPH-104, on Day 15, Day 45. Anti-RPH-104 antibody concentrations will be assessed.
Pharmacokinetic variables:	
 
Change in serum hs-CRP levels at 24, 72 hours, 5, 6, 15, 29 and 45 days after start of the investigational product therapy compared to baseline.
 

	• Change in serum amyloid protein A levels at 24, 72 hours, 5, 6, 15, 29 and 45 days after start of the investigational product therapy compared to baseline.
	
 
Change in serum cytokine (IL-1α, IL-1β, IL-1RA, IL-6, IL-8, TNF-α) levels at 24, 72 hours, 5, 6, 15, 29 and 45 days after start of the investigational product therapy compared to baseline.
 

Safety variables:	Adverse events, laboratory results, vital signs, physical examination findings, ECG findings.
Statistical methods:	Data analysis
	Descriptive statistics of continuous variables will be presented using means,

CONFIDENTIAL P. 16 of 84

Sponsor Name: R-Pharm International LLC
Investigational medicinal product provided by the
Sponsor:
RPH-104/L04018
Name of the active ingredient:
RPH-104/L04018

median, 25th and 75th percentiles, standard deviation, minimum, maximum, number of observations available. Categorical data will be presented as absolute and relative values for each category. Time to event parameters will be plotted using Kaplan-Meier curves.

Efficacy analysis

The primary efficacy variable will be analyzed by analysis of covariance using baseline and treatment group as covariates. Other continuous efficacy variables will be analyzed using repeated measures ANOVA. Efficacy variables representing time to event will be compared using a log rank test.

The pharmacokinetic, pharmacodynamic and immunogenicity parameters of RPH-104, as well as safety of the therapy with the investigational products will be assessed using descriptive statistics methods.

Interim data analysis

Due to the low patient recruitment rate in the study and the adverse impact of the COVID-19 pandemic on the recruitment, at the decision of the sponsor, an interim analysis of the data of 47 patients included in the study as of November 2020 will be carried out in order to assess the feasibility of continuing recruitment and further conducting the study. All patients whose data will be included in the interim analysis completed their participation in the study; follow-up is not required in the study. The interim analysis will include the efficacy, safety, pharmacokinetics and pharmacodynamics data available and verified at the time of analysis. No changes in the declared statistical methods in connection with the interim analysis are planned. The dose dependence of the pharmacokinetics and pharmacodynamics of the investigational product, as well as the main efficacy measures (reduction in pain intensity) will be studied using descriptive statistics, a confidence interval approach, and graphical methods. The safety analysis will be carried out using descriptive statistics methods. Formal testing of hypotheses is not planned in the study. In view of the exploratory nature of the study, no corrections for multiple comparisons are planned.

Sample size justification

Fourteen (14) patients per group will allow constructing 95% confidence intervals around the mean change in pain intensity on a visual analogue scale at 72 hours after the start of the investigational product use in each group with an accuracy of 30 mm change in pain intensity.

In addition, this sample size will allow establishing statistically significant differences between the groups in pairwise comparisons, without control for type I error for multiple comparisons, taking into account the type I error  $\alpha = 5\%$ , if the difference between the compared groups is  $\geq 20$  mm. The sample size was calculated assuming a standard deviation of 26 mm for change in pain intensity at 72 hours.

CONFIDENTIAL P. 17 of 84

# 3 STUDY FLOW CHART

 Table 3.1
 Schedule of the study procedures

	Прескрининг1	]	Day :	1			D2	D3	D4	D5	D6	D10	D15	D18	D22	D29	D45	D60	BRM	FUV
Procedure/time (hours)		Screening 		2	4	8	24	48	72	96	120	216 ± 1 day	336 ± 1 day	408 ± 1 day	504 ± 1 day	672 ± 1 day	1056 ± 1 day	± 7 days		
Time window for evaluation of PK, PD, overall pain intensity in the assessed joint, and patient global assessment of efficacy				n	±10	es	± ho	2 urs	±	3 hou	ırs				, -					
Visit (V); Telephone call (T)	V	B27					V	V	V	V	V	В3	V	В3	В3	V	V	Т		
Handing over the patient information sheet with information about the study to the patient, informing the patient about the study procedures and possible participation	X																			
Signing of the Informed Consent Form	X1	X4																		
Medical history collection		X																		
Tuberculosis risk assessment questionnaire		X																		
Recording concomitant/previous therapy 		X										X Thro	ughout th	e study	•					X
Collection of demographics 		X																		
Efficacy and pharmacodynam	ic assessment																			
Pain intensity in the assessed joint 		X7	X8	X	X29	X	X	X	X	X	X	X26	X	X26	X26	X	X		X25	
Patient global assessment of efficacy 			X8	X	X29	X	X	X	X	X	X	X26	X	X26	X26	X	X		X25	
Health assessment questionnaire (HAQ) 		X																		
Assessment of the degree of swelling, tenderness, erythema		X					X	X	X	X	X	X	X	X	X	X	X			

CONFIDENTIAL P. 18 of 84

	Прескрининг1	I	Day :	1			D2	D3	D4	D5	D6	D10	D15	D18	D22	D29	D45	D60	BRM	FUV
D d (b		Screening 		_	_	0	24	40	73	0.0	120	216 ± 1	336 ± 1	408 ± 1	504 ± 1	672 ± 1	1056 ± 1	± 7		
Procedure/time (hours)		Screening	0	2	4	8	24	48	12	96	120	day	day	day	day	day	day	days		
Time window for evaluation																				
of PK, PD, overall pain																				
intensity in the assessed joint, and patient global assessment					±10		_	-2												
of efficacy					inute	es		urs	±3	3 hoi	ırs									
and movement restriction in the																				
assessed joint by physician 																				
High-sensitivity (hs) CRP 		X					X		X	X	X		X			X	X			
Serum amyloid protein A 		X					X		X	X	X		X			X	X			
Cytokines (IL-1α, IL-1β, IL-1RA, IL-6, IL-8, TNF-α) 		X					X		X	X	X		X			X	X			
Recording the timing of rescue therapy																			X25	
Diagnosis of infections: HIV, HBsAg, HCV Ab 		X																		
Diagnosis of tuberculosis (T-SPOT.TB) 		X22																		
Blood samples for pharmacokinetic assessment 			X	X		X	X	X	X	X	X	X	X	X	X	X	X			X
Anti-drug antibodies 			X														X			X
Serum pregnancy test for women of childbearing potential		X															X			X
Clinical laboratory tests 		X14								X			X				X			X
Urinalysis with sediment microscopy (site laboratory) 		X								X			X				X			X
Physical examination 		X											X				X			X
Vital signs 		X					X		X	X	X		X		X	X	X			X
Weighing										X			X				X			X
12-lead ECG		X14								X							X			X
Chest X-ray in 2 views		X14,17																		
Adverse event recording		X18	X	X	X	X	X	X	X	X	X	X	X	X	X	X	X	X		X

CONFIDENTIAL P. 19 of 84

	Прескрининг1	I	Day 1	1			D2	D3	D4	D5	D6	D10	D15	D18	D22	D29	D45	D60	BRM	FUV
Procedure/time (hours)		Screening 	0	2	4	8	24	48	72	96	120	216 ± 1 day	336 ± 1 day	408 ± 1 day	504 ± 1 day	672 ± 1 day	1056 ± 1 day	± 7 days		
Time window for evaluation of PK, PD, overall pain intensity in the assessed joint, and patient global assessment of efficacy				m	±10	es	± ho	2 urs	±3	3 hou	ırs									
Eligibility assessment		X																		
Randomization			X																	
Subcutaneous administration of RPH-104 			X																	
Assessment of injection site reactions 			X 	X	X	X	X	X	X	X	X	X	X	X	X	X	X			
First dosing Dispensing of Voltaren® (diclofenac) and Ortanol® (omeprazole) 20			$X^{28}$																	
Dispensing of Voltaren® (diclofenac) and Ortanol® (omeprazole) for self-administration 			$X^{28}$																	
Use of rescue medication Kenalog 												Σ	ζ							
Handing over the Patient Diary 			X				X	X	X	X	X	X	X	X	X	X				
Patient diary collection							X	X	X	X	X	X	X	X	X	X	X			

D – day, CRP – C-reactive protein, PK – Pharmacokinetics, PD – pharmacodynamics (in this study, these are hsCRP, serum amyloid protein A, cytokines), BRM – before the administration of rescue medication, FUV – follow-up visit for early discontinuation of the patient from study

- 1. At pre-screening, the patient is informed about the study procedures, signs the informed consent to participate in the pre-screening, and is given the patient information sheet with informed consent form describing the main study for familiarization.
- 2. Screening procedures must be performed within 24 hours and the patient is randomized during this time. If necessary (in exceptional cases), the screening period can be extended, while randomization had to be carried out no later than 120 hours (5 days) after the onset of an attack.

CONFIDENTIAL P. 20 of 84

- 3. Visits to the study site on Study Days 10, 18 and 22 are required for patients receiving RPH-104; Patients receiving Voltaren® (diclofenac) do not have to come to the study site, but they must fill out the patient diary and patient questionnaires on these days (pain in the assessed joint, patient global assessment of efficacy).
- 4. Informed consent to participate in the study must be obtained and the informed consent form for participation in the study be signed prior to starting any study procedure.
- 5. This includes date of birth, sex, race, weight, height, body mass index, and information on alcohol consumption.
- 6. The patient is given questionnaires at the visits to record pain intensity in the assessed joint on the visual analogue scale (VAS), patient global assessment of efficacy, and scores of the health assessment questionnaire.
- 7. The VAS must be completed twice: the first time at the screening to assess the patient's eligibility and the second time before randomization to obtain a baseline value. Re-assessment of pain intensity in the assessed joint must be performed immediately (within 1 hour) before randomization.
- 8. Assessment of pain intensity and global efficacy assessment must be performed prior to taking blood samples. It is necessary to hand over a questionnaire to the patient for assessment of pain intensity and global efficacy assessment after 15, 30, 45 minutes, (interval  $\pm$  5 min) 1 and 1.5 hours (interval  $\pm$  10 min) after the use of the investigational products.
- 9. The physician assesses the degree of swelling, tenderness, erythema and movement restriction in the assessed joint using the categorical scales specified in this protocol.
- 10. hs-CRP, serum amyloid protein A, cytokines, HIV, HBsAg, HCV Ab, T-SPOT.TB tests, pharmacokinetics and anti-drug antibodies (including the test for neutralizing antibodies) are performed in central laboratories.
- 11. For the diagnosis of infections (HIV, HBsAg, HCV Ab), blood serum samples will be sent to the central laboratory. In addition, rapid tests for the diagnosis of HIV, hepatitis B and C are performed at the screening. Rapid test results should be evaluated prior to patient randomization. Patients suspected of having HIV, hepatitis B or C on the basis of rapid test results should not be randomized.
- 12. Administration of RPH-104, assessment of injection site reactions, blood sampling to assess the pharmacokinetics of the investigational product and anti-drug antibodies will be performed only for patients randomized to receive RPH-104.
- 13. These include: complete blood count (hemoglobin, hematocrit, erythrocytes, platelets, total WBC count with WBC differential in %, absolute neutrophil count), blood chemistry: sodium, potassium, chlorine, magnesium, calcium, phosphorus, bicarbonates, BUN (or urea), uric acid, total protein, albumin, glucose, creatinine with estimation of creatinine clearance using the Cockcroft-Gault formula, bilirubin (total and direct), AST, ALT, alkaline phosphatase, LDH, amylase, lipase, GGT, creatine kinase, MB-creatine kinase; blood lipids (cholesterol, triglycerides, LDL, HDL); coagulation tests (fibrinogen, INR, aPTT). Complete blood count and creatinine test at screening and on Study Days 5, 15, 45 and with early discontinuation of the patient from the study are performed at the local laboratory of the study site. Blood chemistry tests with blood lipids and coagulation tests are performed in the central laboratory.
- 14. The results of ECG, chest x-ray in 2 views, creatinine level, absolute neutrophil count, leukocyte and platelet counts should be assessed prior to patient randomization. To be included in the study, the patient has to meet the study eligibility criteria based on these data.

CONFIDENTIAL P. 21 of 84

- 15. Physical examination includes: assessment of overall health, skin (presence of rash or lesions), head, mouth, eyes, ears, throat, nose, lungs (auscultation), heart (auscultation for murmurs, gallop rhythm, pericardial friction rubs), lower extremities (peripheral edema, presence of varicose veins), abdomen (palpation and auscultation), nervous system (mental status, gait, reflexes, motor and sensory functions, coordination) and lymph nodes.
- 16. This includes: body temperature, blood pressure, respiratory rate and heart rate in a sitting position after 5 minutes at rest.
- 17. Chest X-ray in 2 views is performed at screening if the patient does not have results of chest X-ray in 2 views or fluorography of the chest in 2 views or chest CT performed within 3 months before the expected date of the first injection of the investigational product;
- 18. Serious adverse events are recorded from the time of signing the informed consent to participate in the study. Other adverse events are recorded from the time of administration to the patient (the first intake by the patient) of the investigational product.
- 19. In patients receiving RPH-104, the assessment of injection site reactions is carried out 15, 30, 45 minutes (interval ± 5 min) after administration and then in accordance with the table of study procedures. The physician assesses the presence of tenderness, redness, swelling, induration, hemorrhage and itching at the RPH-104 injection site. The patient is assessed for these reactions at each visit. They are recorded as adverse events.
- 20. Voltaren® (diclofenac) and Ortanol® (omeprazole) are dispensed only for patients receiving Voltaren® (diclofenac).
- 21. In the diaries, patients record information about the development of adverse events and changes in concomitant therapy (discontinuation or dose change) or use of new concomitant therapy. Patients receiving Voltaren® (diclofenac) are also given additional diaries to record information about the use of Voltaren® (diclofenac). The diaries are filled in by patients when they are outside the study site.
- 22. Blood sampling for T-SPOT.TB test should be carried out either at screening, or during the time the patient is in the hospital.
- 23. Urine analysis includes: color, transparency, specific gravity, pH level, glucose, protein, ketone bodies, bilirubin, urobilinogen, nitrites. Analysis of urine sediment includes: leukocyte count, erythrocyte count, epithelial cell count with cell type, and bacterial count.
- 24. Information is collected about all previous therapy for the primary disease—gout, information about other prior therapy is collected for a period of 30 days before the start of screening.
- 25. Patients who do not tolerate pain receive the rescue medication after 2 hours and until Day 45 of the study after the first use of rescue medication Kenalog® (triamcinolone) to intensify therapy. If it is necessary to use the rescue medication, immediately before its use, an unscheduled assessment of pain severity using a visual analogue scale (VAS) and global assessment of efficacy is to be performed and the time of use of the rescue medication is to be registered.
- 26. If patients receiving Voltaren® (diclofenac) miss visits on Day 10, 18 and 22, they record pain intensity in the assessed joint and the patient global assessment of efficacy at home. For this purpose, they are given patient questionnaires to take home at Visits on Days 6 (1 score) and 15 (2 scores).
- 27. By the decision of the investigator, after the use of the investigational products, patients can be hospitalized and remain under observation in the hospital. All procedures in accordance with the visit schedule for these patients are carried out in a hospital setting. Patients who, in the investigator's opinion, are not eligible for hospitalization, are followed up for at least 3 hours after the investigational product administration, after which they can leave the study site and continue to participate in the study with all assessments performed on an outpatient basis.

CONFIDENTIAL P. 22 of 84

- 28. At the visit on Day 1, all patients in the Voltaren® (diclofenac) group are given the drug for dosing at the study site; patients who are hospitalized by the decision of the investigator are given the drug in a hospital setting before being discharged; subsequently, these patients are given the drug in an amount sufficient for self-administration at home in accordance with the study protocol. Patients who are not eligible for hospitalization receive the drug for self-administration on Day 1 after the rest of the procedures and assessments.
- 29. Patients receiving Voltaren® (diclofenac) on an outpatient basis are allowed to leave the study site 3 hours after taking the drug. In this case, they are given patient questionnaires (measurement of pain in the assessed joint, patient global assessment of efficacy) to fill at home 4 and 8 hours after taking the drug.
- 30. New patient diaries are issued as needed.

CONFIDENTIAL P. 23 of 84

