# 9.5 Dose, method of administration, dosing regimen, and duration of therapy

## 9.5.1 Use of the investigational product RPH-104

RPH-104 is administered to patients randomized to one of the RPH-104 groups. The dose of RPH-104 for administration to a patient is selected based on information on the patient's therapy group.

To administer RPH-104 4 mg to a patient, 0.1 mL of RPH-104 solution is injected to the patient. To administer RPH-104 20 mg to a patient, 0.5 mL of RPH-104 solution is injected to the patient. To administer RPH-104 40 mg, 1 mL of RPH-104 solution is injected to the patient. To administer RPH-104 80 mg, 2 mL of RPH-104 solution is injected to the patient. To administer RPH-104 160 mg, the patient received two injections of 2 mL RPH-104 solution at different injection sites (Table 9.1).

RPH-104 is injected subcutaneously into the anterior abdominal region in one of the areas indicated in Figure 9.1.

CONFIDENTIAL P. 44 of 84

	U
Treatment group	Volume of RPH-104 solution for administration to the patient
RPH-104 4 mg	0.1 mL
RPH-104 20mg	0.5 mL
RPH-104 40 mg	1 mL
RPH-104 80mg	2 mL
RPH-104 160 mg	Two 2 mL injections at different injection sites

Table 9.1 Injected volume of RPH-104 to patients

[figure not shown]

Figure 9.1 Areas of the anterior abdominal wall where RPH-104 should be administered.

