## Day 10 (216 hours after the start of therapy) and Day 18 (408 hours after the start of therapy)

- Blood sampling for the following analyses:
  - Assessment of RPH-104 pharmacokinetics (only for patients randomized to the RPH-104 groups, central laboratory);
- Dispensing questionnaires to the patient to record the following:
  - o Pain intensity in the assessed joint according to VAS;
  - o Patient global assessment of the efficacy using a categorical scale.
- Assessment of the degree of swelling, tenderness, erythema and movement restriction in the assessed joint;
- Evaluation of RPH-104 injection site reactions (only for patients who received RPH-104);
- Collecting information on concomitant therapy and adverse events;
- Patient diary collection and registration of entered data;
- Handing over the Patient Diary.

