#### 13.6.1 Adverse events

Adverse events occurring starting from the time of investigational product administration (start of use) until 45 days after the investigational product administration will be considered treatment-emergent adverse events.

Serious adverse events developing between the signing by the patient of the Informed Consent Form for participation in this study and the administration of the investigational medicinal product will be regarded as pre-treatment SAEs.

Adverse event data will be coded using the last version of the MedDRA medical terminology. Frequency rates of adverse events during the study therapy will be calculated for each organ system, by primary diagnosis, investigational product dose, and absolute and relative amounts of patients developing adverse events. Summary data reflecting the severity of adverse events will be presented by organ system and primary disease. Adverse events related to the investigational product ('possibly related,' 'probably related,' and 'definitely related') will be presented separately.

Summary data reflecting withdrawals from the study due to adverse events will be presented by organ system and primary disease.

Serious adverse event data will be presented as listings and summary data by organ system and primary disease.

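### Adverse events are ascertained unequally between RPH-104 and diclofenac, and the planned any-AE and related-AE totals make no allowance for it

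*Combined protocol and SAP*

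**What the plan says.** All references are to the combined protocol and SAP.

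- **Visits.** Note 3 to Table 3.1: "Visits to the study site on Study Days 10, 18 and 22 are required for patients receiving RPH-104". Patients on diclofenac "do not have to come to the study site, but they must fill out the patient diary and patient questionnaires on these days".
- **AE collection at those visits.** Section 10.2, Days 10 and 18, lists "Collecting information on concomitant therapy and adverse events". Day 22 has the same item.
- **Diary.** Note 21, which applies to both treatments: "In the diaries, patients record information about the development of adverse events and changes in concomitant therapy".
- **Injection-site checks.** Note 12 restricts these to RPH-104. Under note 19, "the assessment of injection site reactions is carried out 15, 30, 45 minutes" after dosing and then follows Table 3.1. The note adds: "The patient is assessed for these reactions at each visit. They are recorded as adverse events".
- **160 mg regimen.** Section 9.5.1: at this dose "the patient received two injections of 2 mL RPH-104 solution at different injection sites".
- **Analysis.** Section 13.6.1 plans frequencies by organ system and product dose, including "absolute and relative amounts of patients developing adverse events", with related AEs shown separately. It does not mention injection-site reactions or the difference in visits.

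Two sets of passages disagree about Day 1. Section 10.2 heads the 2, 4 and 8 hour procedures, AE collection included, as applying to RPH-104 patients only, whereas the AE row of Table 3.1 has no such limit. Section 10.2 also lists only the 15-minute injection-site check, where note 19 has three early checks.

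**The concern.** Under section 12.1, AEs come to light through spontaneous complaints, interview, examination and tests. An arm with fewer contacts has fewer chances of having an event recorded. Diclofenac is taken for 12 days (section 9.5.2), and after Day 6 the next required visit is Day 15, so the second half of that course has no scheduled investigator contact. RPH-104 patients are seen on Day 10. Day 22 vital signs, where a clinically significant abnormality is an AE (section 11.5.4), are also taken at a visit that diclofenac patients may skip.

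Solicited injection-site findings then add to the patient-level totals in the RPH-104 arms only. The any-AE and related-AE rates could therefore show an excess on RPH-104, or conceal one on diclofenac, partly because of how events were sought. Section 4 says the interim report may become final, so these tables may be the trial's whole safety result.

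**Working it through.** The plan states no number of AE contacts or injection-site checks, so there is no figure of its own to reproduce. The counts below come from Table 3.1, its notes and section 10.2.

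**1. Scheduled AE collection after randomization.**
- RPH-104: times 0, 2, 4, 8 h (4) + Days 2–6 (5) + Days 10, 15, 18, 22, 29, 45 (6) + Day 60 call (1) = 16.
- Diclofenac under note 3: 16 − 3 = 13.
- Diclofenac if the section 10.2 headings also govern: 13 − 3 = 10.
- Section 13.6.1 counts treatment-emergent AEs to 45 days. Without the Day 60 call the counts are 15 against 12 or 9.

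The gap is three contacts, or up to six.

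**2. Injection-site checks (RPH-104 only).** 15, 30, 45 min (3) + 2, 4, 8 h (3) + Days 2–6 (5) + Days 10, 15, 18, 22, 29, 45 (6) = 17. The count is 15 if the Day 1 list in section 10.2 governs. Of the 17, 6 fall on Day 1, 8 at visits both treatments attend (Days 2–6, 15, 29, 45) and 3 at the extra visits.

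**3. What three extra interviews might add to any AE.** Let p be the share of patients who have a recorded AE anyway, and d the chance that one extra interview finds an AE that the diary missed and later visits would not recover. With independence, gain = (1 − p) × [1 − (1 − d)³]. Take d = 5–10%, an assumption with no source in the documents: 1 − 0.95³ = 14% and 1 − 0.90³ = 27%.

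| p | Gain, percentage points |
|---|---|
| 0 (upper bound) | 14 to 27 |
| 30–50% (assumption) | 7 to 19 |
| 70% (7/10 on placebo, Table 4.2) | 4 to 8 |
| 88% (22/25 on RPH-104, Table 4.2) | 2 to 3 |

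Table 4.2 concerns healthy volunteers, whose rates may not carry over to patients with gout.

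**4. What injection-site reactions might add.** If a share q of RPH-104 patients react, independently of other AEs, gain = (1 − p) × q. With q = 5–20% and p = 30–50% (both assumed), the range runs from 0.50 × 0.05 = 2.5 points to 0.70 × 0.20 = 14 points. Table 4.2 lists no injection-site-reaction term among 25 dosed volunteers. The nearest entry is one soft tissue inflammation at 160 mg. That does not exclude a low rate, but gives no support for a high one.

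**5. Two injections at 160 mg.** With per-injection risk r, the per-patient risk is 1 − (1 − r)² if the injections react independently, and r if they always react alike. For an assumed r of 10–20%, that is 19–36% at one extreme and 10–20% at the other.

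**6. Scale.** In an arm of 14, one patient is 1/14 = 7 points, and 7/14 (50%) has an exact 95% interval of 23% to 77%.

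**The case against.** The strongest reply is that the plan already has compensating collection. Diclofenac patients keep an AE diary, are asked about AEs again at the shared Day 15, 29 and 45 visits, and are telephoned on Day 60. Onset dates are recorded. Events around Days 10, 18 and 22 are thus mostly collected later rather than lost. Laboratory tests, ECGs and physical examinations are scheduled on the same days for both treatments. This stands, and it shrinks the gap. It does not close it: self-report and later recall are not the same method as an interview, and section 10.2 qualifies the diary on these days as applicable only in some cases.

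Second, injection-site reactions are real effects of an injected regimen, not artefacts of the schedule, and two injections are part of the 160 mg treatment as defined. This also stands. The reactions belong in the safety results. The difficulty is only that a combined total mixes them with events that could occur on either treatment.

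Third, the organ-system tables and individual listings allow the reactions to be separated, safety is descriptive (section 13.7), and section 13.1.7 announces a separate, fuller analysis plan. Organ-system rows, however, do not give the number of patients with any other AE, because a patient may appear in several rows. Descriptive rates are still read across arms. The fuller plan is the natural place for the change.

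**Conclusion.** The concern holds for the comparison of RPH-104 with diclofenac: ascertainment differs by three scheduled AE contacts, or up to six, and by up to 17 (or 15) solicited checks specific to RPH-104. The direction is towards higher any-AE and related-AE totals on RPH-104.

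The size is not known from the documents. The ranges worked above rest on assumed detection and reaction rates. The 14 to 27 points are an upper bound that requires no patient to have any other AE and nothing to be recovered later. The 19–36% at 160 mg requires an assumed reaction risk and independent injections.

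A reader might infer that AE rates cannot be compared across any arms, or that the schedule could produce a dose trend. The documents do not support either. All five RPH-104 doses follow one visit schedule, so they remain comparable with each other. The one exception is the second injection at 160 mg, which bears on injection-site reactions and is a true feature of that regimen. This is a matter of reporting and even-handed collection in an exploratory, open-label study; it does not invalidate the safety analysis.

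**What to change.** 1. In section 13.6.1 or the separate analysis plan, tabulate patients with any AE and with related AEs, by arm, both with and without injection-site reactions. Report those reactions per patient and per injection. No new data are needed.
2. Reconcile the section 10.2 headings for 2, 4 and 8 hours with the AE row of Table 3.1, and the Day 1 injection-site list with note 19, so that AE collection on Day 1 is the same in all arms. Then add AE incidence over the shared-visit period to Day 6, as a supplementary table only: it covers about half of the 12-day diclofenac course and less than one RPH-104 half-life (about 10 days, section 4.3.2). For patients already treated, if Day 1 collection did differ, that table should start from the Day 2 visit.
3. If recruitment continues, ask diclofenac patients the same AE question by telephone on Days 10, 18 and 22. Otherwise, state the unequal contact schedule as a limitation of the RPH-104 versus diclofenac AE comparison.

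**Cost.** Items 1 and 2 lengthen the safety tables slightly, and the reconciliation is a text change. Item 3 needs a small amendment and about 13 calls. If Period 1 filled as planned (22 patients, 7 on diclofenac) and the 2:2:2:2:1 ratio held, the 47 enrolled include 47 − 22 = 25 in Period 2, of whom 25/9 = 2.8 are on diclofenac. That leaves 14 − 9.8 = 4.2 to recruit, and 4.2 × 3 ≈ 13.
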